This prospective research clinical trial will be conducted in a single academic medical center. The enrollment period is between January 1st, 2022 and December 31st, 2023. The initial follow-up period will be closed on December 31st 2023 with a continuation of the follow-up until December 31st 2024. Patients will be selected from current LVAD patients followed by our medical center clinic and from patients implanted with LVAD at our center during the study enrollment timeframe. Patients will be randomly assigned to the control protocol and the silver protocol. Both protocols will be taught to the patients and nursing staff by the VAD coordinators. The comparative evaluation will be done through adverse event collection, driveline culture results, patient survey and DL photos at specific intervals.

A. Inclusion Criteria

The following patients will be included in the study:

- >18 years of age
- Implanted with LVAD as DT or BTT at the Academic Medical Center with implantation scheduled between January 1st, 2022 and December 31st, 2023
- Implanted prior to January 1st 2022 with no history or signs and symptoms of DLI as of January 1st 2022.

B. Exclusion criteria

The following will be excluded from the study. Patients with

- A history of DLI
- A history of sternal wound infection
- Implantation secondary to VAD exchange for device infection

C. Interventions

A new driveline dressing kit will be trialed on patients randomized to the intervention arm of the study. Both arms will have a regular dressing kit and a sensitive dressing kit.

The trial arm kits include:

- a. For standard dressing: a silverlon antimicrobial patch, CHG swabs for cleaning, an occlusive dressing with window, and driveline anchors. The driveline dressing change frequency will be weekly.
- b. For sensitive skin dressing: a silverlon antimicrobial patch, Providone/iodine swabs for cleaning, an occlusive dressing with window, and sensitive driveline anchors. The driveline dressing change frequency will be weekly.

The control arm kits include:

- a. For standard dressing: No antimicrobial barrier, CHG swabs for cleaning, an occlusive dressing with window, and driveline anchors. The driveline dressing change frequency will be every 96 hours.
- b. For sensitive skin dressing: No antimicrobial barrier, Providone/iodine swabs for cleaning, an occlusive dressing with window, and driveline anchors. The driveline dressing change frequency will be every 96hr.

D. Assessment

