The following endpoints will be assessed for patients in both arms of the study enrolled between 01/01/2022 and 12/31/2023 and comparison will be drawn between the 2 groups:

- 1. DLI rate in number per 100-patient month
- 2. Time to first DLI in days

E. Data Management

Data is collected by the PI and analyzed by our data analyst. Additionally, cost data will be collected via our purchasing analyst who will retain data on number ok kits sent to each patient. Patients will be deidentified for all data collection. Data is stored behind the medical center firewall and encryption software. Data is accessible to the PI, the data analyst and our medical director.

F. Statistical Analysis Plan (SAP)

Study Design:

A randomized controlled trial (RCT) in which patients are randomly assigned to one of two groups:

- a. Silver Dressing Group
- b. Standard Dressing Group

Primary Outcome:

 Rate of driveline infection in number per 100 patient month, defined as number of driveline cultures positive for bacterial infection per 100 months of patients on support.

Secondary Outcome(s):

 Mean time to first driveline infection, defined as a number of days to first positive culture.

Covariates to Control for:

- Body Mass Index (BMI)
- Gender

INTERMACS Level

Statistical Analysis Overview:

The analysis will focus on univariate tests to assess the differences between silver dressing and standard dressing groups, while controlling for covariates such as BMI, gender, and INTERMACS level. The significance level for all analyses will be set at p < 0.05.

Data Cleaning and Assumptions:

- Missing data will be addressed using appropriate techniques, such as multiple imputation or complete case analysis, depending on the nature and extent of missing data.
- Assumptions of normality will be assessed for continuous variables, and non-parametric tests will be considered for non-normally distributed data.

Univariate Analysis:

- For continuous outcomes, descriptive statistics (mean, standard deviation) will be presented
 for each treatment group. Between-group comparisons will be made using a two-sample ttest (if data are normally distributed) or a Mann-Whitney U test (if data are non-normally
 distributed).
- For categorical outcomes, descriptive statistics (frequencies and percentages) will be presented for each group. Between-group comparisons will be conducted using the chisquare test or Fisher's exact test, as appropriate.

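### The primary outcome counts every positive culture, with no masking described and control sites scheduled to be uncovered 1.75 times as often, so detection can differ by arm

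*Combined protocol and SAP*

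**What the plan says.** Section F (SAP), Primary Outcome, sets the DLI rate as the primary measure, "defined as number of driveline cultures positive for bacterial infection per 100 months of patients on support". The secondary outcome rests on the same event: "Mean time to first driveline infection, defined as a number of days to first positive culture".

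Section C (Interventions) gives the schedules. For the silver kits, "The driveline dressing change frequency will be weekly". For the standard control kit, "The driveline dressing change frequency will be every 96 hours", and for the sensitive-skin control kit, "The driveline dressing change frequency will be every 96hr". Every kit has a windowed occlusive dressing. Only the silver kits add a patch.

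On who knows the assignment, Methods says "Both protocols will be taught to the patients and nursing staff by the VAD coordinators". On ascertainment, it says "The comparative evaluation will be done through adverse event collection, driveline culture results, patient survey and DL photos at specific intervals"; the intervals are not listed and no photo finding is linked to taking a culture. On data handling, section E says "Data is collected by the PI and analyzed by our data analyst".

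The documents do not say on what signs, when or by whom a culture is taken, or how repeat cultures of one infection are counted. They describe no masked or adjudicated classification. The planned sensitivity analyses cover missing data and outliers only, and the adjustment covariates are BMI, gender and INTERMACS level.

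**The concern.** An event exists only if someone swabs the site. The kits and schedules differ visibly, so patients and nurses will know the arm, and the control site is scheduled to be uncovered more often. Brief drainage or redness seen and swabbed at a control change could come and go between two weekly silver changes.

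This is a question of whether an infection is found, which is separate from whether the dressing prevents it. Randomisation does not protect against it, because the difference arises after assignment. The planned covariate adjustment and sensitivity analyses would not reveal it. Both outcomes depend on the same cultures, so agreement between them would not be independent support. The Objective expects the silver protocol to lower the DLI rate, and that is also the arm with fewer scheduled looks.

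**Working it through.** The plan states no sample size, expected event count, effect size or power, so there is no figure of its own to reproduce. The inputs are the two change intervals in section C. The share f and the total number of positive cultures D are assumptions, shown as ranges.

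**1. Scheduled looks.** Weekly is 7 × 24 = 168 hours, and 168/96 = 1.75 (inverse 0.571). Per year this is 365/4 = 91.25 changes in control and 365/7 = 52.1 in silver. Per 100 patient-months of 30.4375 days, it is 3043.75/4 ≈ 761 and 3043.75/7 ≈ 435.

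**2. Rate ratio with no true effect.** Suppose a share f of positive cultures scales with the number of changes and the rest do not depend on it. The apparent silver-to-control ratio is (1 − f) + f/1.75 = 1 − 0.429f.

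**3. Chance of a false significant result for silver.** This uses an exact conditional binomial test, two-sided 0.05, with equal person-time. The SAP does not specify this test; it only gives a sense of scale.

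| f | Ratio, no true effect | Apparent reduction | D = 20 | D = 40 | D = 60 | D = 100 |
|---|---|---|---|---|---|---|
| 0 | 1.00 | 0% | 2.1% | 1.9% | 1.4% | 1.8% |
| 25% | 0.893 | 10.7% | 3.7% | 4.3% | 3.8% | 6.2% |
| 50% | 0.786 | 21.4% | 6.6% | 9.5% | 10.0% | 18.3% |
| 100% | 0.571 | 42.9% | 20.7% | 37.1% | 47.1% | 74.4% |

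**4. What f = 100% would require.** Suppose signs are seen only at changes and start at a random point in the interval. A sign lasting d days is then seen with probability min(1, d/4) in control and min(1, d/7) in silver. The silver-to-control ratio is 0.571 for d up to 4 days, 5/7 = 0.71 at 5 days, 6/7 = 0.86 at 6 days, and 1.00 from 7 days on. So the full 0.57 needs every counted sign to last 4 days or less. A persistent infection is caught in both arms.

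**5. Time to first DLI.** If infections are found only at changes, the mean wait is half the interval: 7/2 = 3.5 days in silver and 4/2 = 2.0 in control. The difference is 1.5 days, or 1.5/365 = 0.4% of a year.

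**The case against.** The strongest reply has four parts.

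- **Size.** Nothing in the documents ties cultures to dressing changes, so 1.75 is a ratio of scheduled changes, not of cultures taken. Step 4 shows that persistent infections are not lost, and the time shift is negligible against follow-up that may run for years. This stands: 0.57 is the extreme case, not an expectation.
- **Direction.** Because cultures are counted and not episodes, later detection in silver could produce more repeat positives there. Knowing the arm could also prompt more swabbing of a new kit. This stands in part. Fewer looks make a bias towards silver the likelier direction, but not a certain one.
- **Visibility.** Both arms have a window, which allows inspection between changes. This stands as a mitigation of unknown strength. A reader might infer that the silver patch hides the exit site; the documents do not say so.
- **Design.** Weekly change is part of the protocol under test, so unequal intervals are not themselves a fault. This also stands. The weakness is an outcome whose counting rule is not independent of those intervals or of knowing the arm.

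A reader might go further and conclude that a lower silver rate would be a detection artefact, or that both outcomes are materially biased. The documents support neither. They show that the rate can be biased by an amount they do not let us estimate, and that the effect on timing is minor.

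**Conclusion.** The point holds in limited form, as a should-fix. With no masking described, no culture rule, and control sites scheduled to be uncovered 1.75 times as often, the stated count can give a rate ratio away from 1 with no true effect, probably in favour of silver. The size is 1 − 0.429f: modest at f = 25% (0.89), appreciable at 50% (0.79), and 0.57 only at the limit.

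This rests on three things: that the trial is open, which is inferred from visibly different kits and the absence of any described masking; that changes follow the schedule; and an f that the documents do not supply. Brief or colonising positives, repeat cultures of one episode and unmasked decisions to swab are where the bias would mainly come from.

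**What to change.** Leave both dressing schedules as they are and amend the SAP:

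- **(a) Endpoint.** Count infection episodes, each once, that have a positive culture plus documented signs from a pre-specified list identical in both arms. This replaces counting all positive cultures.
- **(b) Classification.** Have existing staff classify events from de-identified records with arm, dressing type and kit counts withheld, since the last two would reveal the arm.
- **(c) Visibility of looking.** Report cultures taken, positive and negative, per 100 patient-months by arm, with setting and reason where recorded. This shows directly whether looking was unequal.
- **(d) Sensitivity analysis.** Where records allow, restrict to events identified at assessments timed the same in both arms. The interval photos are a candidate, but their timing is not listed and no visit schedule is documented, so feasibility has to be checked first.

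Items (a) and (b) do not equalise looks: a sign seen only because the dressing was off still qualifies, and a culture never taken cannot be recovered. State residual detection bias as a limitation.

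The document is dated 03/24/2025 and planned follow-up ran to December 31st 2024. If follow-up has ended, all of this has to be done by chart abstraction. The cost is some abstraction work and slightly fewer events, and the reason for some cultures may not have been recorded.

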- Univariate analysis will focus on comparing the primary and secondary outcomes between the two treatment groups, without adjusting for covariates.

Multivariate Analysis (Controlling for Covariates):

- Linear regression will be used to compare the treatment effects while adjusting for BMI, gender, and INTERMACS level. These covariates will be included as fixed effects in the model.
- The significance level for all covariates will be set at p < 0.05 in the final model, following a backward elimination procedure, if necessary, to identify the most relevant covariates.

Model Assumptions and Diagnostics:

The assumptions for each regression model will be checked. For linear regression, normality
of residuals, linearity, and homoscedasticity will be assessed.

Sensitivity Analyses:

 Sensitivity analyses will be conducted to evaluate the robustness of the results by varying handling strategies for missing data and by testing the impact of potential outliers.

Statistical Software:

• All analyses will be conducted using SAS version 9.4.

Data Handling and Quality Assurance

- Data is collected by the PI and analyzed by our data analyst. Patients are deidentified for all data collection. Data is stored behind the medical center firewall and encryption software. Data is accessible to the PI, the data analyst and our medical director.
- Outliers and implausible values will be reviewed and resolved.

Reporting

- Results will be reported in accordance with CONSORT guidelines.
- Findings will be disseminated through peer-reviewed publications and conference presentations.

[figure not shown]
Conclusion:

The statistical analysis will provide insight into the comparative effectiveness of silver dressing versus standard dressings while controlling for potential confounders such as BMI, gender, and INTERMACS level. The univariate analysis will provide preliminary insights into dressing effect,

with multivariate models ensuring a more rigorous adjustment for confounding variables. All analyses will be conducted at a significance level of p < 0.05.

References

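### Mean days to first positive culture has no value for never-infected patients, and the SAP gives neither a censoring rule nor a time-to-event method, so the result turns on an unstated choice

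*Combined protocol and SAP*

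**What the plan says.** Under Secondary Outcome(s), the SAP (section F) defines its one secondary outcome as "Mean time to first driveline infection, defined as a number of days to first positive culture". Section D, Assessment, lists it as "Time to first DLI in days". The Objective mentions further secondary goals, such as dermatitis and cost, but the SAP does not take them up.

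For continuous outcomes, the Univariate Analysis section says: "Between-group comparisons will be made using a two-sample ttest (if data are normally distributed) or a Mann-Whitney U test". It adds: "Univariate analysis will focus on comparing the primary and secondary outcomes between the two treatment groups, without adjusting for covariates". The only adjusted model, under Multivariate Analysis, is linear regression. Missing data are covered by one sentence: "Missing data will be addressed using appropriate techniques, such as multiple imputation or complete case analysis". That list is given by way of example, and the SAP does not say whether an absent infection date counts as missing. The sensitivity analyses vary missing-data handling and outliers; none concerns censoring.

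Methods sets the calendar: "The enrollment period is between January 1st, 2022 and December 31st, 2023" and "The initial follow-up period will be closed on December 31st 2023 with a continuation of the follow-up until December 31st 2024". Section A also admits patients "Implanted prior to January 1st 2022 with no history or signs and symptoms of DLI as of January 1st 2022". The available text gives no start day for the count, no censoring rule and no survival method.

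**The concern.** A mean of days to first positive culture exists only for patients who have a positive culture. With 24 months of staggered entry and a calendar close, many patients will reach the end of follow-up uninfected, and bridge-to-transplant patients may leave support first. The Objective cites infection rates from 10% to 50%. If those applied here, 50% to 90% of patients would have no value.

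The analyst must then decide what to do with these patients, and the SAP does not say. The most direct reading of a mean uses infected patients only. That group is selected by outcome after randomisation, and patients whose infection was prevented drop out of the comparison. At stake is one uninformative secondary result that could be misread as showing no delay in infection. The start day is also open: for a patient implanted before 2022 it could be implantation or randomisation, which may lie far apart.

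**Working it through.** The documents state no sample size, power, hazard or effect size, so there is no planned figure to reproduce. The check shows how far the result depends on the unstated handling.

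**Inputs from the documents:** entry 1 January 2022 to 31 December 2023; close 31 December 2023, continued to 31 December 2024; significance level 0.05.

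**Assumed inputs (base case):** 50 or 100 patients per arm, 1:1, two-sided test; control hazard 0.02 per month (2 per 100 patient-months); hazard ratio 0.5, so silver 0.01; leaving support 0.02 per month; half the patients under follow-up from 1 January 2022, the rest entering evenly over 24 months; close 31 December 2024; 30.4375 days per month. Potential follow-up C is then 36 months for half, and uniform on 12 to 36 months for the rest.

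**Step 1: who has a value.** With infection hazard h and total hazard λ = h + 0.02, P(infected by C) = (h/λ)(1 − exp(−λC)).
- Control, λ = 0.04: C = 36 gives 0.5 × (1 − 0.2369) = 0.382. Uniform C gives 0.5 × (1 − (0.6188 − 0.2369)/0.96) = 0.301. Average 0.341.
- Silver, λ = 0.03: C = 36 gives (1 − 0.3396)/3 = 0.220. Uniform C gives (1 − (0.6977 − 0.3396)/0.72)/3 = 0.168. Average 0.194.

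So 66% of controls and 81% of silver patients have no value. Expected infections are 50 × (0.341 + 0.194) ≈ 27, or about 54 with 100 per arm.

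**Step 2: mean days among the infected.** Mean = E[T; T ≤ C] / P(infected), where E[T; T ≤ C] = (h/λ)[1/λ − (C + 1/λ)exp(−λC)].
- Control: 5.274 (C = 36) and 3.131 (uniform), average 4.202; 4.202/0.3413 = 12.31 months = 375 days.
- Silver: 3.263 and 1.843, average 2.553; 2.553/0.1938 = 13.17 months = 401 days.

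Halving the hazard moves this mean by only 26 days, because the fixed close cuts off late infections in both arms.

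**Step 3: censoring day used as the value.** The mean is the average of (1 − exp(−λC))/λ.
- Control: (19.08 + 15.06)/2 = 17.07 months, about 519 days.
- Silver: (22.01 + 16.75)/2 = 19.38 months, about 590 days.
- An arm with no infections at all (λ = 0.02): (25.66 + 18.76)/2 = 22.21 months, about 676 days. At the 2023 close it would be (19.06 + 10.29)/2 = 14.68 months, about 447 days.

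An infection-free arm would thus score 676 or 447 days purely according to the closing date. The figure largely reflects length of follow-up.

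**Step 4: power by handling** (simulation, base case):

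| Handling of never-infected patients | 50 per arm | 100 per arm |
|---|---|---|
| Dropped; t-test | 6% | 6% |
| Dropped; Mann-Whitney | 5% | 6% |
| Censoring day as value | about 16% | about 29% |
| Ranked last; Mann-Whitney | about 39% | about 67% |
| Log-rank | about 42% | about 70% |

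Repeat runs of the third row gave 15–18% and 29–32%. The log-rank row agrees with Schoenfeld's approximation, Φ(√(D/4) × ln 2 − 1.96): D = 26.8 gives 43%, and D = 53.5 gives 72%.

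**Step 5: range.** Control hazards of 1, 2, 3 and 5.8 per 100 patient-months were tried with both closing dates and both sizes. The ends correspond to 12-month risks of 1 − exp(−0.12) = 11% and 1 − exp(−0.696) = 50%, near the ends of the Objective's 10% to 50% if that is read as a 12-month risk. Infected-only t-test power was 4–24%, infected-only Mann-Whitney 3–22% and log-rank 19–95%.

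**Step 6: no effect.** With hazard ratio 1 in the base case, every handling in the table rejected in about 5% of trials.

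**Step 7: competing events.** With both control hazards at 0.02, one minus Kaplan-Meier is 1 − exp(−0.02T): 21.3% at 12 months and 38.1% at 24. Cumulative incidence with leaving support as a competing event is 0.5(1 − exp(−0.04T)): 19.1% and 30.9%.

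**The case against.** The strongest reply is that the SAP never says that never-infected patients are dropped, and that one of its own named tests can work. Mann-Whitney with never-infected patients ranked last comes close to log-rank in the base case. This stands. A reader might infer that the outcome has almost no power whatever is done; the documents do not support that. The loss depends on the handling, and the handling is what is missing. Ranking last does not rescue the outcome as defined, though, because it yields no mean. It also treats short and long infection-free follow-up alike.

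A reader might also infer that multiple imputation must invent infection dates for patients observed infection-free. That is too broad. Imputation constrained to times after the censoring day could be valid; the SAP simply does not specify it. Ordinary imputation does not respect that limit. In a separate simulation (100 per arm, hazard ratio 0.5, no loss from support), 62–86% of days drawn from a normal distribution fitted to the infected fell before the patient's own censoring day.

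A third inference is that the plan could show silver to be harmful. That needs a constructed hazard shape. With a silver hazard of 2 per 100 patient-months to month 6 and 0.5 after it, infected silver patients average 264 days against 375, although 18% against 34% are infected. The infected-only t-test is then significant against silver in 16% / 29% of trials. Nothing in the documents suggests this shape, and under the other two handlings such results almost vanish (0–0.1%). Across the Step 5 range, infected-only tests were significant against silver in at most 2% of trials.

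**Conclusion.** The concern holds in a limited form. The secondary outcome is undefined for never-infected patients, the plan's calendar makes such patients certain in practice, and no method named for a number of days handles censoring. That much needs no assumed number. The size does: with a true hazard ratio of 0.5 in the base case, power runs from about 6% to about 39% at 50 per arm, and from about 6% to about 67% at 100 per arm, depending on a choice the SAP leaves open. Log-rank gives about 42% and 70%. All of these rest on assumed sample size, hazards, entry pattern and loss from support.

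Two further inferences should be resisted. This is not a source of false positives while censoring is equal in both arms. Nor does it touch the primary outcome, a rate per patient-months of support. It should be fixed, as a defect in one secondary result.

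**What to change.** Replace the mean with time to first positive driveline culture, analysed as a time-to-event outcome, and state:

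- **Start of the clock:** randomisation, or implantation if that comes later. Patients implanted before 2022 start at randomisation. The condition is needed because section A admits patients whose implantation is only scheduled, and the text does not say whether randomisation can precede it.
- **End of the clock:** censor at withdrawal and at 31 December 2024; treat death, transplant and explant as competing events.
- **Exclusion from general rules:** the t-test, Mann-Whitney, linear regression and imputation rules do not apply to this outcome.
- **Reporting:** cumulative incidence by arm allowing for competing events, a log-rank test, and a cause-specific Cox hazard ratio adjusted for BMI, gender and INTERMACS level. With roughly 27 to 54 events in the base case, the adjustment can carry few parameters.
- **Optional:** the 12-month difference in cumulative incidence with its 95% confidence interval. Enrolment to the end of 2023 and a close at the end of 2024 give 12 months of potential follow-up from enrolment.

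The cost is SAP wording and a little more work with standard SAS procedures (PROC LIFETEST, PROC PHREG). Each patient's randomisation date, implantation date, and date of and reason for end of support are needed. The document is dated 03/24/2025, after the last closing date, so the change should be dated and should state whether outcomes by arm had been seen.

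### The primary outcome is a person-time rate, but the SAP's tests and linear regression carry no exposure offset or weight

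*Combined protocol and SAP*

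**What the plan says.** The SAP (Primary Outcome) defines the endpoint as "Rate of driveline infection in number per 100 patient month, defined as number of driveline cultures positive for bacterial infection per 100 months" on support. Section D (Assessment) lists it as "DLI rate in number per 100-patient month". Both describe events over accumulated time, not a measurement taken once per patient.

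For the unadjusted analysis, the SAP states: "Univariate analysis will focus on comparing the primary and secondary outcomes between the two treatment groups, without adjusting for covariates". Two families of test are offered. For continuous outcomes: "Between-group comparisons will be made using a two-sample ttest (if data are normally distributed) or a Mann-Whitney U test". For categorical outcomes: "Between-group comparisons will be conducted using the chisquare test", or Fisher's exact test. The SAP does not say to which family the rate belongs.

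For the adjusted analysis, the Multivariate Analysis section names one model: "Linear regression will be used to compare the treatment effects while adjusting for BMI, gender, and INTERMACS level". Its dependent variable is not given. The Conclusion leans on this step, "with multivariate models ensuring a more rigorous adjustment for confounding variables".

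On timing, Methods states: "The enrollment period is between January 1st, 2022 and December 31st, 2023". Follow-up first closes on 31 December 2023 and then continues to 31 December 2024. Patients already on support and new implants are both eligible, whether destination therapy or bridge to transplant.

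No offset, exposure weight, Poisson or negative binomial model appears in the readable text. One figure after the Reporting section could not be read and is not counted either way.

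**The concern.** A person-time rate needs an analysis that knows how long each patient was observed. Here the months differ by design, yet they appear only in the denominator of the outcome definition. The analyst must choose a patient-level variable: the count of positive cultures, an any-infection indicator, or each patient's count divided by months. The first two ignore exposure. The third uses it, but the t-test and linear regression then give every patient equal weight, although a rate seen over 1 month is far noisier than one seen over 24.

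At stake are the precision of the primary comparison, the meaning of the estimate, and whether a second analyst could reproduce the primary result from the SAP. If months on support also differed between arms, some of the permitted choices would no longer be valid tests.

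**Working it through.** The plan gives no sample size, control rate, effect size or loss rate, so there is no figure of its own to reproduce.

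**1. Exposure from the dates.** Entry on 1 January 2022 gives at most about 24 months at the first close and 36 at the second. Entry on 31 December 2023 gives 0 and 12. The ranges of maximum exposure are therefore 0–24 and 12–36 months, before death, transplant or withdrawal.

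**2. The variable changes the estimate.** Take two patients with one event each, one seen for 1 month and one for 24.
- Mean of patient rates: (100/1 + 100/24)/2 = 52.1 per 100 patient-months.
- Pooled rate: 100 × 2/25 = 8.0.

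**3. Why equal weighting loses precision.** With Poisson events at rate λ and months T, a patient's rate has variance λ/T. For n patients:
- mean of patient rates: variance (λ/n) × mean(1/T);
- pooled rate: variance (λ/n)/mean(T).

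The ratio is mean(T) × mean(1/T). Assume uniform exposure:
- 0.5–24 months: mean(T) = 12.25 and mean(1/T) = ln(48)/23.5 = 0.165. The ratio is 2.02, so the SD is 1.42 times as large. Simulated SDs, 100 per arm at 2 per 100 patient-months: 0.58 against 0.41.
- 12–36 months: mean(T) = 24 and mean(1/T) = ln(3)/24. The ratio is 1.10, so the SD is 1.05 times as large. Simulated: 0.29 against 0.28.

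The loss of precision comes from short follow-up.

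**4. Power by simulation.** All inputs are assumed: 100 per arm, control rate 2 per 100 patient-months, rate ratio 0.5, half the patients already implanted and the rest entering evenly over 24 months, covariates without effect. Each pair is an unweighted analysis of patient rates against a person-time analysis.

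| Setting | Month 24 | Month 36 |
|---|---|---|
| Unadjusted, 2% monthly loss | about 40% vs 60% | about 58% vs 76% |
| Adjusted, 2% monthly loss | 39% vs 55% | 56% vs 74% |
| Unadjusted, no loss | gap about 15 points | 86% vs 89% |
| Adjusted, no loss | 52% vs 65% | 84.5% vs 86.0% |

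The adjusted pairs compare linear regression with Poisson regression, which was replaced by a permutation test below 20 events. With 50 per arm and 2% loss they are 24% vs 28% and 34% vs 41%. With 50 per arm, no loss and month 36, the order reverses: 55.9% vs 53.4%.

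Against Mann-Whitney on patient rates, the person-time rule gains −3 to +7 points. If one infection yields three positive cultures on average, each counted (100 per arm, 2% loss, month 36), linear regression has 51%, the person-time rule 66% and Mann-Whitney 69%.

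**5. Type I error.** With equal loss, the named tests give 1.4–5.8%. Now assume loss of 1% against 3% per month and no true effect (100 per arm, rate 2). Mean months are 16.2 vs 13.4 at month 24 and 25.7 vs 19.4 at month 36. Counts then show spurious ratios of 13.4/16.2 = 0.83 and 19.4/25.7 = 0.75. Type I error at month 24 / 36:
- linear regression on counts: 10.6% / 24.2%;
- Fisher's exact test: 8.2% / 19.1%;
- Mann-Whitney on patient rates: 8.8% / 14.9%.

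Over all scenarios with this loss, the t-test and linear regression on patient rates stay at 4.0–5.6%, and the person-time rule at 3.1–5.2%.

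**The case against.** The strongest reply is that each patient's own rate is the obvious variable, that it does use months, and that tests on it are valid when exposure is similar in both arms. Moreover, patient rates will be mostly zero, so the SAP's own normality rule sends the unadjusted comparison to Mann-Whitney, which gives up little or no power. The large gaps apply to the t-test and linear regression, and at month 36 they nearly vanish without loss. This is also a single-centre plan with a feasibility aim. All of that stands, and it limits the size of the point.

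It does not remove the point. The SAP never says that the patient rate is the variable. Mann-Whitney gives neither a rate ratio nor covariate adjustment. For adjustment the SAP names only linear regression, the method with the precision loss.

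Three stronger inferences are tempting, and the documents support none of them:
- **That the named tests generally produce false positives.** They do so here only if months on support differ between arms. The hypothesis of fewer allergic reactions and more comfort with silver does not establish this: the denominator is time on the device, discomfort with a dressing does not end support, and both arms have a sensitive-skin kit.
- **That infection shortens support and so biases the result.** The Objective lists infection among the burdens that limit life expectancy, but gives no figure. In simulation the absolute difference in patient rates is then inflated, but their ratio stays at 0.50–0.51 against a true 0.50.
- **That the analysis was chosen with results in hand.** The document date (03/24/2025) follows the last follow-up date. The text does not say whether outcomes by arm had been seen.

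**Conclusion.** The point holds as a gap between a person-time outcome and analyses with no exposure offset or weight. It should be fixed, but it does not by itself make the named tests invalid. The mismatch and the unequal exposure follow from the text and the dates alone.

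The size is conditional. It is material when many patients have short follow-up, through early closing or loss, and the t-test or linear regression is used: roughly 15 to 20 points of power with 100 per arm under the stated assumptions. It is slight at month 36 without loss, smaller in small trials, and small or nil against Mann-Whitney. Any inflation of type I error depends on unequal months on support, which the documents do not establish.

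**What to change.** For the primary outcome, replace linear regression and the t-test / Mann-Whitney with the following:

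- **Model.** Poisson (log-link) regression of events per patient, with log(months on support since randomisation) as offset, arm as factor, and BMI, gender and INTERMACS level as covariates. Use small-sample-corrected robust standard errors and report the rate ratio with 95% CI. The robust errors matter: with strong clustering within patients (gamma variance 2), plain Poisson errors gave 9–17% type I error in simulation, against 4–6% with robust errors.
- **Fallback.** If events are too few for the adjusted model to fit, use an unadjusted permutation test of the pooled person-time rates. Fix the switch rule blind to arm. In simulation with 30 per arm, the adjusted model failed to fit in 6% of trials at 20 expected events and in 66% at about 7.
- **Counting.** Start exposure at randomisation, also for patients already implanted. Say which closing date ends it. Count repeat positive cultures from one infection once, or rely on the robust errors. Counting once also avoids the power loss from clustered cultures.
- **Dating.** Date the change and state whether outcomes by arm had been seen.

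The cost is SAP wording and a different procedure in SAS 9.4, which the SAP already names. No new patients are needed. The downsides are that the fallback is unadjusted and any event cut-off rests on assumed inputs. When the covariates have no effect, the rule can have up to 12 points less power than a plain permutation test used throughout.
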